2.1. Study Objectives

2.1.1. Primary Objective

[figure not shown]
The primary objective of this Phase 2a study is to evaluate the efficacy of PH94B Nasal Spray (PH94B) administered 4 times per day over 4 weeks for the treatment of anxiety in adult subjects with adjustment disorder with anxiety (AjDA).

2.1.2. Secondary Objective

The secondary objective of the study is to evaluate safety and tolerability of PH94B.

2.1.3. Exploratory Objective

An exploratory objective of the study is to evaluate efficacy of PH94B over time during the 4-week treatment period.

2.2. Study Endpoints

2.2.1. Efficacy Endpoints

2.2.1.1. Primary Efficacy Endpoint

The primary efficacy endpoint is mapped to the primary objective as follows:

Primary Objective

The primary objective of this Phase 2a study is to evaluate the efficacy of PH94B administered 4 times per day over 4 weeks for the treatment of anxiety in adult subjects with AjDA.

Primary Efficacy Endpoint

The primary efficacy endpoint of the study is change from baseline in anxiety level as measured by the Hamilton Anxiety Scale (HAM-A) at the end of the 4-week treatment period.

2.2.1.2. Secondary Efficacy Endpoint(s)

The secondary efficacy endpoints are mapped to the primary objective as follows:

Primary Objective

The primary objective of this Phase 2a study is to evaluate the efficacy of PH94B administered 4 times per day over 4 weeks for the treatment of anxiety in adult subjects with AjDA.

Secondary Efficacy Endpoints

Secondary efficacy endpoints of the study include the following:

Individual subject improvement as assessed by the Clinical Global Impression-Improvement (CGI-I) scale. Values for comparison will be the proportion of “responders” in each group, defined as subjects receiving scores of 1 (Very much improved) or 2 (Much improved) at the end of treatment with PH94B.

Individual subject improvement as assessed by the subject’s self-assessment of improvement (by Patient Global Impression of Change [PGI-C] scale) at the end of treatment compared to baseline. Values for comparison will be the proportion of “responders” in each group, defined as subjects receiving scores of 1 (Very much improved) or 2 (Much improved) at end of treatment with PH94B.

Individual subject improvement on the Adjustment Disorder New Module (ADNM) scale at the end of treatment compared to baseline.

Individual subject improvement on the International Adjustment Disorder Questionnaire (IADQ) at end of treatment compared to baseline.

2.2.1.3. Exploratory Efficacy Endpoint(s)

The exploratory efficacy endpoints are mapped to the exploratory objective as follows:

Exploratory Objective	Exploratory Efficacy Endpoints
An exploratory objective of the study is to evaluate efficacy of PH94B over time during the 4-week treatment period.	Summaries and changes from baseline in HAM-A at Weeks 1, 2, and 3. Summaries and changes from baseline in ADNM subscales at Week 4. Summaries of CGI-I and PGI-C at Weeks 1, 2, 3, and 4 (each week).

2.2.2. Safety Endpoints

The safety endpoints are mapped to the secondary objective as follows:

Secondary Objective	Safety Endpoints
The secondary objective of the study is to evaluate the safety and tolerability of PH94B.	Incidence and severity of adverse events (AEs), AEs leading to discontinuation, and serious adverse events (SAEs). Changes in clinical laboratory values. Changes in 12-lead electrocardiogram (ECG) results. Changes in physical examination findings. Changes in vital signs results. Changes in Montgomery-Asberg Depression Rating Scale (MADRS) scores. Changes in suicidal ideation scores, as documented using the Columbia Suicide Severity Rating Scale (C-SSRS).

3. Overall Study Design and Plan

3.1. Overall Design

This is a double-blind, placebo-controlled, parallel group, Phase 2a clinical study in adult subjects diagnosed with AjDA. Subjects diagnosed with AjDA by the Diagnostic and Statistical Manual of Mental Disorders, 5th Edition (DSM-5) criteria and a HAM-A of 20 or greater are to be enrolled.

3.2. Experimental procedures

[figure not shown]
Subject participation in the Study will last a total of 6 to 10 weeks, depending on the duration of the screening period and whether they need a washout of concomitant anxiolytics. Upon signing an investigation review board approved informed consent, all subjects will complete Visit 1 (Screening) and enter a screening period [REDACTED] that could include tapering of concomitant anxiolytics, if necessary. Visit 1 (Screening) will consist of subject demographics recording, safety assessments (medical and psychiatric history, prior and concomitant medications recording, physical examination, vital signs, ECG, blood tests and urinalysis, urine drug screen, urine pregnancy test [if appropriate]) and psychiatric assessments (Mini-International Neuropsychiatric Interview [MINI], MADRS, HAM-A, Liebowitz Social Anxiety Scale [LSAS], Clinical Global Impression-Severity [CGI-S], and C-SSRS) to determine eligibility. Subjects will then return to complete Visit 2 (Baseline). At this visit, subjects will complete all psychiatric assessments (ADNM, IADQ, MADRS, HAM-A, CGI-S, C-SSRS), adverse event recording, concomitant medications recording, vital signs, blood tests and urinalysis, urine drug screen, and urine pregnancy test (if appropriate). If the subject continues to meet the inclusion criteria and none of the exclusion criteria, the subject will be randomized 1:1 to PH94B or placebo. The subject will be trained on using the investigational product (IP) and will be dispensed a 1-week supply of PH94B or placebo. Subjects will then commence 4 weeks of double-blind treatment with the randomized IP four times per day.

Subjects will return for weekly site visits (Visits 3, 4, and 5), in which the subject will return the IP vial dispensed at the previous visit and receive a new vial. At Visits 2, 3, 4, and 5, when the subjects will be dispensed 2 vials of the appropriate IP, the vial weights will be recorded before dispensing to a subject. Study personnel will also record the weight of all returned vials. Concomitant medications and adverse events (AEs) will be recorded. During these visits, the HAM-A, PGI-C, CGI-I, CGI-S, and C-SSRS will be completed. Vital signs will be collected, and nasal passages will be examined.

When the subject returns for Visit 6 (End of Treatment), besides the assessments completed at Visits 3 through 5, the subjects will also complete the MADRS, ADNM, and IADQ; and have a physical examination, ECG, blood tests and urinalysis, urine drug screen, and urine pregnancy test (if appropriate). Any remaining IP vials will be collected.

The subject will then come back after a one-week washout period for Visit 7 (Follow-up). During this visit, AEs concomitant medications since the last visit, and vital signs will be collected. In addition, the HAM-A, C-SSRS, and 20-item Physician Withdrawal Checklist (PWC-20) will be administered.

Subjects who discontinue prior to Visit 6 (End of Treatment), will undergo a Visit 6 (Early Termination) visit, and provide all Visit 6 outcome measures and safety assessments for the efficacy analysis.

3.4. Study Population

The study population includes males and females, age ≥ 18 years, with a current diagnosis of AjDA as defined in the Diagnostic and Statistical Manual of Mental Disorders, 5th Edition.

3.5. Treatments Administered

Subjects will receive one of the treatments listed in Table 1 at Visit 2 (Baseline).

Table 1: Treatment Definitions

Treatment Description	Treatment Abbreviation
PH94B nasal spray self-administered as an intranasal solution in the amount of [REDACTED] to each nostril for a total dose of 3.2 μg [REDACTED]. Dose is to be administered 4 times per day separated by at least 2 hours (targeting morning, noon, early evening, and bedtime).	PH94B
Placebo nasal spray self-administered as an intranasal solution in the amount of 100 μL to each nostril for a total of 200 μL . Spray is to be administered to each nostril 4 times per day separated by at least 2 hours (targeting morning, noon, early evening, and bedtime).	Placebo

3.6. Method of Assigning Subjects to Treatment Groups

At Visit 2 (Baseline), subjects who meet study entry criteria will be randomly assigned to placebo or PH94B in a 1:1 ratio at each study site. The randomization schedule will be computer generated using a permuted block algorithm to randomly allocate IP to randomization numbers,

stratified by study site. A central interactive web response system (IWRS) will assign randomization numbers sequentially to subjects that are entered into the study. The randomization schedule will be prepared by Premier Research before the start of the study. No one involved in the study performance will have access to the randomization schedule before official unblinding of treatment assignment. No subject will be randomized into this study more than once.

3.7. Blinding and Unblinding

This is a double-blind study throughout. All subjects, investigators, and study personnel involved in the conduct of the study, including data management, will be blinded to treatment assignment with the exception of a specified unblinded statistician and a member of the Interactive Response Technology team from Premier Research who will have access to the randomization code. Unblinded study personnel will not participate in study procedures or data analysis prior to the official unblinding of the study data to all study-related personnel. If an interim analysis is to be conducted, then unblinded personnel who are not otherwise involved in the study will prepare the data for review.

Study personnel will make every effort to safeguard the integrity of the study blind to minimize bias in the conduct of the study. Treatment unblinding is discouraged if knowledge of the treatment assignment will not materially change the planned management of a medical emergency. Unblinding will be permitted in a medical emergency that requires immediate knowledge of the subject's treatment assignment. All IP containers will be provided with a code that will unblind the contents in an emergency. Procedures for emergency unblinding will be outlined in the Study Procedures Manual for PH94B-CL029.

The Investigator or designee will record the date and reason for treatment unblinding on the appropriate electronic case report form (eCRF) for that subject. If treatment assignment is unblinded for an individual subject, study personnel will be notified of that subject's treatment assignment without unblinding the treatment assignments for the remaining subjects in the study. Thus, the overall study blind will not be compromised. Overall unblinding will take place at the end of the study only after database lock has been achieved.

3.8. Schedule of Events

Please see protocol PH94B-CL029, A Phase 2a Double-blind, Placebo-controlled, Parallel Study of PH94B Nasal Spray in the Treatment of Anxiety in Adults with Adjustment Disorder with Anxiety for a detailed schedule of events.

4. Statistical Analysis and Reporting

This study is considered a Phase 2a exploratory study under an Investigational New Drug (IND) application for PH94B targeting AjDA. Statistical tests will be applied and interpreted to determine feasibility and best approaches for potential Phase 2b and Phase 3 studies.

The final study analysis will be conducted only after all subjects have completed the study as

described in the referenced protocol, a thorough blind review of all collected data has been conducted and approved, and a final SAP has been approved and signed prior to unblinding of the data.

4.1. Introduction

Data processing, tabulation of descriptive statistics, calculation of inferential statistics, and graphical representations will primarily use Statistical Analysis System Software (SAS) (release 9.4 or higher). If the use of other software is warranted, the final SAP and the statistical methodology report will detail what software was used for what purposes.

Continuous (quantitative) variable summaries will include the number of subjects (n) with non-missing values, mean, SD, median, minimum, and maximum. The minimum and maximum will be reported with the same degree of precision (i.e., the same number of decimal places) as the observed data. Measures of location (mean and median) will be reported to 1 degree of precision more than the observed data and measures of spread (SD) will be reported to 2 degrees of precision more than the observed data.

Categorical (qualitative) variable summaries will include the frequency and percentage of subjects who are in the category or each possible value. The denominator for the percentage calculation will be based upon the total number of subjects in the study population for the treatment groups unless otherwise specified. Percentages will be presented to 1 decimal place. Counts of zero will be presented without percentages.

Unless otherwise indicated, all statistical tests will be conducted at the 0.05 significance level using 2-tailed tests, and p values will be reported. Corresponding 95% confidence intervals (CIs) will be presented for statistical tests. All p values will be displayed in four decimals and rounded using standard scientific notation (e.g., 0.XXXX). If a p value less than 0.0001 occurs it will be shown in tables as < 0.0001 ; similarly, if a p value greater than 0.9999 occurs, it will be shown in tables as > 0.9999 . Confidence intervals will be reported to 1 degree of precision more than the observed data.

This study is considered a Phase 2a exploratory study under an IND application for PH94B targeting AjDA. Statistical tests will be applied and interpreted to determine feasibility and best approaches for potential Phase 2b and Phase 3 studies.

4.2. Interim Analysis and Data Monitoring

No interim analyses or data monitoring are planned.

5. Analysis Populations

The following analysis populations are planned for this study:

- **All Subjects Population:** All subjects who sign an informed consent, participate in a Visit 1 (Screening), and are entered into the eCRF will be included in the All Subjects

population. The All Subjects population will be used for summaries of subject disposition.

- **Safety Population:** The Safety population includes all subjects who are dispensed IP and reported administering at least 1 dose of IP. The Safety population will be used for safety analyses. For analyses of the Safety population, each subject will be analyzed by the actual treatment received, even if it differs from the subject's randomized treatment assignment.
- **Intent-to-Treat (ITT) Population:** The ITT population includes all subjects who are randomized and have one documented dose of IP at Visit 2 (Baseline). The ITT population will be used for efficacy analyses. For analyses of the ITT population, each subject will be analyzed by their randomized treatment assignment, even if the subject did not receive the assigned treatment or did not follow the protocol until completion.

Assignment of subjects to populations will be confirmed at a blinded data review meeting to be held before the study database is locked. All protocol deviations that occur during the study will be considered for their severity/impact and will be taken into consideration when subjects are assigned to analysis populations.

6. General Issues for Statistical Analysis

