13.1.1 Analysis Populations

The following 2 analysis populations are planned for this study:

- Intent-to-treat (ITT) population: All subjects who are randomized and have documented one dose of IP at Visit 2 will be included in the ITT population. All efficacy analyses will be performed using the ITT population.
- Safety population: All subjects who are dispensed IP and reported administering at least one dose of IP will be included in the safety population. All safety analyses will be performed using the safety population.

Inclusion in the analysis populations will be determined prior to database lock.

If a subject is randomized incorrectly or is administered the incorrect IP, analyses of the ITT population will be based on the assigned treatment whereas all other analyses will be based on the actual treatment.

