8.1.1. Sensitivity Analyses of the Primary Efficacy Endpoint

8.1.1.1. Complete Case Sensitivity Analysis

Should imputation of the primary endpoint be necessary, a complete case analysis will be performed in the ITT population. The complete case analysis will be exactly parallel to the planned primary efficacy analysis, except it will exclude any subjects with missing change from baseline to Visit 6 HAM-A total scores, using only observed responses. Descriptive summaries will be provided for the primary endpoint based on the complete-case data.

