Subject ID	Randomization		Actual Treatment	Analysis Populations		Primary Reason(s) for Exclusion	
	Date (Study Day)	Number		Treatment	Safety [1]		ITT [2]
XXXXXX	DDMMYYYY (XX)	XXXX	XXXXX	XXXXX	Yes	No	ITT: Subject was not randomized and/or did not administer at least one dose of IP at Visit 2 (Baseline).
XXXXXX	DDMMYYYY (XX)	XXXX	XXXXX	XXXXX	Yes	Yes	
XXXXXX	DDMMYYYY (XX)	XXXX	XXXXX	XXXXX	Yes	Yes	
XXXXXX	DDMMYYYY (XX)	XXXX	XXXXX	XXXXX	No	No	Safety: Subject did not administer at least one dose of IP.

Abbreviations: IP = investigational product; ITT = intent-to-treat.

Note: Study day is calculated relative to the date of first dose of study drug. Subjects were randomized 1:1 to receive 4 weeks of either PH94B or placebo 4 times daily.

[1] The Safety Population includes all subjects who were dispensed IP and reported administering at least 1 dose of IP.

[2] The ITT Population includes all subjects who were randomized and had 1 documented dose of IP at Visit 2 (Baseline).

Programming note: Concatenate reasons for exclusion with a semi-colon. Sort by planned treatment and subject ID. Add abbreviations as needed depending on what is displayed.

Listing 16.2.4.1
 Subject Consent and Demographics
 All Subjects

Actual Treatment: XXXXXXXXXXXX

Subject ID	Date Informed Consent Signed/ Protocol Version	Date of Birth	Age (years)	Sex	Child- Bearing Potential?	Date of Last Menstrual Period Known?	Date of Last Menstrual Period	Ethnicity	Race	Weight (kg)	Height (cm)	BMI (kg/m ²)
XXXXXX	DDMMYYYY/ XXXXXXXXXX	DDMMYYYY	XX	Male				XXXXXX	XXXXXX	XX.X	XX	XX
XXXXXX	DDMMYYYY/ XXXXXXXXXX	DDMMYYYY	XX	Female	Yes	Yes	DDMMYYYY	XXXXXX	XXXXXX	XX.X	XX	XX
XXXXXX	DDMMYYYY/ XXXXXXXXXX	DDMMYYYY	XX	Male				XXXXXX	XXXXX	XX.X	XX	XX
XXXXXX	DDMMYYYY/ XXXXXXXXXX	DDMMYYYY	XX	Female	No	No		XXXXXX	XXXXXX	XX.X	XX	XX
XXXXXX	DDMMYYYY/ XXXXXXXXXX	DDMMYYYY	XX	Female	Yes	Yes	DDMMYYYY	XXXXXX	XXXXXX	XX.X	XX	XX

Abbreviation: BMI = Body Mass Index.

Programming Note: Concatenate if multiple races selected (e.g., Multiple: XXXX, XXXX). If Asian is selected, concatenate with any selected Asian subcategories (e.g., Asian: XXXX, XXXX).

[figure not shown]
Listing 16.2.4.2
 Medical and Psychiatric History
 All Subjects

Actual Treatment: XXXXXXXX

Subject ID	System Organ Class/ Preferred Term/ Verbatim Term	Start Date (Study Day)/ End Date (Study Day)
XXXXXX	XXXXXXXXXXXXXXXXX/ XXXXXXXXXXXXXXXXX/ XXXXXXXXXXXXXXXXX	DDMMYYYY (XX)/ DDMMYYYY (XX)

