	Visit 5	DDMMYYYY:HHMM (XX)	XXX	XXX/ XXXXXXX/ XX	XXX/ XXXXXXX/ XX	DDMMYYYY:HHMM (XX)	XXX	XXX/ XXXXXXX/ XX	XXX/ XXXXXXX/ XX
	Visit 6 (End of Treatment/Early Termination)					DDMMYYYY:HHMM (XX)	XXX	XXX/ XXXXXXX/ XX	XXX/ XXXXXXX/ XX

Note: Study day is calculated relative to the date of first dose of study drug.

[1] Visit 6 (End of Treatment/Early Termination) includes data from subjects who either completed Visit 6 (End of Treatment) or who discontinued from the study and completed an early termination visit.

Programming Note: If study drug was not dispensed, concatenate reason.

[figure not shown]

Listing 16.2.5.2
Study Drug Administration
All Subjects

Actual Treatment: XXXXXXX

Subject ID	Subject Instructed?	Subject Self-Administer First Dose?/ Reason Not Administered	Date/Time (Study Day) of Administration
XXXXX	XXX	XXX	DDMMYYYY:HHMM (XX)
XXXXX	XXX	XX/ XXXXXXXXXXXX	DDMMYYYY:HHMM (XX)
XXXXX	XXX	XXX	DDMMYYYY:HHMM (XX)
XXXXX	XXX	XXX	DDMMYYYY:HHMM (XX)

Note: Study day is calculated relative to the date of first dose of study drug.

Listing 16.2.6.1
 Hamilton Anxiety Scale (HAM-A)
 All Subjects

Actual Treatment: XXXXXXXX

Subject ID	Study Visit [1]	HAM-A Completed?/ Reason Not Completed	Date/Time of Assessment (Study Day)	Assessment	Result	Baseline Flag [2]
XXXXX	Visit 1 (Screening)	XX/ XXXXXXX				
XXXXX	Visit 2 (Baseline)	XXX	DDMMYYYY/HH:MM (XX)	Anxious mood Tension Fears Insomnia Intellectual Depressed mood Somatic (muscular) Somatic (sensory) Cardiovascular symptoms Respiratory symptoms Gastrointestinal symptoms Genitourinary symptoms Autonomic symptoms Total Score	X = XXXXXXXX X = XXXXXXXX XX	Yes

Abbreviation: CFB = change from baseline; HAM-A = Hamilton Anxiety Scale.

Note: Study day is calculated relative to the date of first dose of study drug. The HAM-A total score is the sum of the individual item scores. CFB is calculated as the difference between the baseline score and the score at the current visit.

[1] Visit 6 (End of Treatment/Early Termination) includes data from subjects who either completed Visit 6 (End of Treatment) or who discontinued from the study and completed an early termination visit.

[2] Baseline is defined as the last non-missing assessment before the first dose of study drug at Visit 2 (Baseline).

Programming Note: If HAM-A was not completed, concatenate reason. Baseline flag is only indicated for the Total Score row. CFB Total Score is only displayed for Visit 3 or later.

Listing 16.2.6.1 (cont.)

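### The ITT set requires a documented Visit 2 dose, so a treated subject whose clinic dose was missed or unrecorded would drop out of every efficacy analysis

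*SAP*

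**What the plan says.** The two documents agree on the definition. Protocol 13.1.1: "All subjects who are randomized and have documented one dose of IP at Visit 2 will be included in the ITT population". SAP section 5: "The ITT population includes all subjects who are randomized and have one documented dose of IP at Visit 2 (Baseline". The Safety population in the same sections needs dispensed IP and one reported dose; it names no visit and does not require the dose to be documented.

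The ITT set carries all of the efficacy work. Protocol 13.1.1: "All efficacy analyses will be performed using the ITT population". SAP section 5: "The ITT population will be used for efficacy analyses". Every table in SAP 13.2 is headed ITT. The sensitivity analyses stay inside the set as well; SAP 8.1.1.1 says "Should imputation of the primary endpoint be necessary, a complete case analysis will be performed in the ITT population".

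The shells provide for a subject who is in Safety but not in ITT. Listing 16.2.3.1 has such a row, with the reason "Subject was not randomized and/or did not administer at least one dose of IP at Visit 2 (Baseline". Listing 16.2.5.2 has a column headed "Subject Self-Administer First Dose?/ Reason Not Administered".

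**The concern.** Membership depends on something that happens after randomization, at one named visit, and on there being a record of it. The label ITT suggests that every randomized subject is included. A reader of the results would not expect a subject who took the spray for four weeks and was rated weekly to be missing from the efficacy tables because of a gap at Visit 2.

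What is at stake is usable randomized data in a trial of 40. The ITT count is also the denominator that decides how missing HAM-A scores are imputed in the primary analysis, so a lapse at Visit 2 could change the primary method as well as the sample size.

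**Working it through.** The plan states no figure on this point to reproduce. The check is a reading of the definitions, followed by arithmetic on the planned sample.

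**1. Can a treated subject be excluded?** Take a subject who is randomized at Visit 2, takes no clinic dose or has none recorded, starts at home and attends Visits 3 to 6.
- Safety (SAP 5): included, because one dose was reported.
- ITT (SAP 5, Protocol 13.1.1): excluded, because there is no documented Visit 2 dose.
- Baseline: available. Protocol 10.2.2 places the HAM-A before randomization and dosing.
- Outcome: available. HAM-A is rated at Visits 3 to 6 (Protocol 10.2.3 and 10.2.4).

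**2. Does another analysis bring the subject back?** No.
- Protocol 13.1.4 allows for another population where specified, but none is specified for any efficacy analysis.
- SAP 7.2 mentions a PP Population without defining it or giving it an analysis.
- Both sensitivity analyses in SAP 8.1.1 are reported on ITT.

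**3. Cost in precision.** Input: 40 subjects randomized 1:1 (Protocol synopsis), taken as 20 per arm.
- One exclusion: 1/40 = 2.5% of the trial, 1/20 = 5% of an arm.
- Standard error ratio: sqrt(40/39) = 1.013, about 1.3%.
- Two exclusions: sqrt(40/38) = 1.026, about 2.6%.

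The visible text gives no effect size or SD, so power can only be illustrated. For an assumed standardized effect of 0.8, a two-sided 0.05 test and n1 + n2 - 3 degrees of freedom, a noncentral-t calculation gives:

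| Per arm | Power |
|---|---|
| 20 / 20 | 0.693 |
| 20 / 19 | 0.681 |
| 20 / 18 | 0.668 |

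Over assumed effects from 0.5 to 1.0, losing one or two subjects costs about 1 to 2.5 percentage points.

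**4. Possible shift in an arm mean.** If the excluded subject's HAM-A change differs from the rest of a 20-subject arm by D points, the arm mean moves by D/20. For an assumed D of 5 to 10, that is 0.25 to 0.5 points.

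**5. Effect on the imputation rule.** SAP 6.1.4 uses group-mean imputation when the missing fraction is at most 0.05 and multiple imputation above that. SAP 6.1.7.2 makes the ITT count the denominator.
- Two missing scores, nobody excluded: 2/40 = 0.0500, group-mean imputation.
- The same two missing, one other subject excluded: 2/39 = 0.0513, multiple imputation.
- Three missing, nobody excluded: 3/40 = 0.0750, multiple imputation.
- Two of those three excluded from ITT: 1/38 = 0.0263, group-mean imputation.

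One or two exclusions can therefore move the primary analysis across the threshold in either direction.

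**The case against.** The strongest reply is that the excluded case should hardly ever arise. Protocol 9 puts the first dose at the site, and Protocol 9.4 and 10.2.2 have the subject take it in front of staff at the visit where randomization occurs. A home start is a deviation, and the shells are templates, not forecasts. This stands, and it keeps the expected number near zero. It does not remove the point, because the rule only operates when that procedure fails. SAP 10.1 also foresees visits disrupted by COVID-19, including remote ones.

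A reader might infer that the rule breaks the randomized comparison. The documents do not support that. Subjects and staff are blinded (Protocol 9.6), the two products look similar (Protocol 9.1), and membership is confirmed at a blinded review before lock (SAP 5). Nothing suggests that a missed or unrecorded first dose would depend on arm. What remains is mainly a small loss of precision.

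A reader might also infer that SAP 5 contradicts itself, since it analyses ITT members by assigned arm "even if the subject did not receive the assigned treatment or did not follow the protocol until completion". That sentence settles which arm a member is analysed in, not who is a member. Protocol 13.1.1 makes the same provision for a subject given the wrong IP, who can still have a documented Visit 2 dose. The two statements are compatible.

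Finally, the exclusion reason in Listing 16.2.3.1 turns on whether the dose was taken, not on whether it was documented. The working test may therefore be milder than the definition. The two wordings should then be brought into line.

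**Conclusion.** The point holds as a defect of definition with a small expected effect. The set called ITT is a modified ITT with an unusually narrow entry condition: a treated, fully assessed, randomized subject can be left out, and no planned analysis restores that subject. Each exclusion costs 2.5% of the sample and about 1.3% in standard error, and one can be enough to change the imputation method of the primary analysis.

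This rests on 20 subjects per arm and on an assumed 0 to 2 affected subjects, a number the documents neither give nor allow to be estimated. The power and mean-shift figures are illustrations under assumed effects.

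**What to change.** In Protocol 13.1.1 and SAP 5, replace the documented Visit 2 dose condition with: *all randomized subjects who took at least one dose of IP at any time, analysed as randomized*. Label the set modified ITT. Make the matching change in the protocol synopsis, the Table 14.1.1 footnote, and the footnote and exclusion reason of Listing 16.2.3.1. The cost is a sentence in each place. It should be done before unblinding, because a later change of analysis set would look data-driven.

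An all-randomized set can be added as a sensitivity analysis, but it costs more. The baseline definition (SAP 6.1.1), study day (SAP 6.1.7.1) and the while-on-treatment strategy (SAP 6.1.4, Table 3) all presuppose a first dose. The plan would have to state the baseline and the missing-outcome handling for subjects who never dosed.
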